1.2 Study Objectives

The study objectives are as follows:

Objectives	Endpoints
Primary Objective	Primary Endpoint

To evaluate the mass of peanut particles that migrate under the dentures during a food occlusion methodology when denture adhesive is applied per continuous strips pattern and when no adhesive is used.	
Mass of peanuts under combined maxillary and mandibular dentures.
Exploratory Objectives	Exploratory Endpoints

To evaluate the mass of peanut particles that migrate under the dentures during a food occlusion methodology when denture adhesive is applied per continuous strips pattern and when no adhesive is used.	
Mass of peanuts under combined maxillary and mandibular dentures.

To evaluate the mass of peanut particles that migrate under the maxillary and mandibular dentures during a food occlusion methodology when denture adhesive is applied per conventional pattern, continuous strips pattern and when no adhesive is used.	
Mass of peanuts under maxillary dentures.Mass of peanuts under mandibular dentures.

To evaluate subject responses to questions during a food occlusion	
Subject completed questionnaire.

Objectives	Endpoints
methodology when denture adhesive is applied per conventional pattern, continuous strips pattern and when no adhesive is used.	

 To explore the performance of a marketed denture adhesive when applied per conventional pattern to no adhesive use for subjects in the low and high Kapur-Olshan subgroups. To explore the relationship between the numbers of subject-reported denture dislodgements when denture adhesive is applied per conventional pattern, continuous strips pattern and when no adhesive is used. 	
 Mass of peanuts under combined maxillary and mandibular dentures in each subgroup (low and high Kapur-Olshan scores). The number of subject reported denture dislodgements during chewing.
Safety	

 To assess the tolerability of marketed denture adhesive (Super Poligrip Free). 	
 Treatment emergent adverse events.

This study is a method development study and therefore there is no formal success criterion.

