2 STUDY OBJECTIVES AND ENDPOINTS

Table 2-1 Study Objectives and Endpoints

Objectives	Endpoints
Primary	
To evaluate the mass of peanut particles that migrate under the dentures during a food occlusion methodology when denture adhesive is applied per conventional pattern.	Mass of peanuts under combined maxillary and mandibular dentures.
Exploratory	
To evaluate the mass of peanut particles that migrate under the dentures during a food occlusion methodology when denture adhesive is applied per continuous strips pattern and when no adhesive is used.	Mass of peanuts under combined maxillary and mandibular dentures.
To evaluate the mass of peanut particles that migrate under the maxillary and mandibular dentures during a food occlusion methodology when denture adhesive is applied per conventional pattern, continuous strips pattern and when no adhesive is used.	Mass of peanuts under maxillary dentures. Mass of peanuts under mandibular dentures.
To evaluate subject responses to 2 questions during a food occlusion methodology when denture adhesive is applied per conventional pattern, continuous strips pattern and when no adhesive is used.	Subject completed questionnaire.
To explore the performance of a marketed denture adhesive when applied per conventional pattern to no adhesive use for subjects in the low and high Kapur-Olshan subgroups.	Mass of peanuts under combined maxillary and mandibular dentures in each subgroup (low and high Kapur-Olshan scores).
To explore the relationship between the number of subject-reported denture dislodgements when denture adhesive is applied per conventional pattern, continuous strips pattern and when no adhesive is used.	The number of subject reported denture dislodgements during chewing.
Safety	
To assess the tolerability of marketed denture adhesive (Super Poligrip Free).	Treatment emergent adverse events.

This study is a method development study and therefore there is no formal success criterion.

Document Name	208397 Clinical Protocol 2.docx	Document Identifier	Effective Date
Type	Version		
eldo_controlled	2.0; Most Recent; Effective; CURRENT	090032d580db1b91	24-Oct-2017 08:49:05

Sodium-calcium mixed partial salt of poly(methylvinylether/maleic acid) and carboxymethylcellulose

208397

Final Clinical Protocol, 20 Oct 2017

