7.1.3 Well-Fit Assessment, Kapur (Olshan Modification) Index

Each denture (upper and lower) will be examined for retention and stability using the Kapur Index (Olshan Modification) ([Kapur, 1967](#); [Olshan, 1992](#)) by an examiner with expert knowledge of prosthodontics. A sum score (upper + lower) of ≥ 6 is required for inclusion.

Retention:

With gloved hands, the examiner will attempt to unseat the upper and lower denture by applying an opposing vertical force at the canine/lateral incisor region of the denture. The examiner will score retention as 0 - 5 using the following criteria:

5= Excellent- denture offers excellent resistance to vertical pull and lateral force.

4= Very Good- denture offers very good resistance to vertical pull and lateral force.

3= Good- denture offers moderate resistance to vertical pull and lateral force.

2= Fair- denture offers moderate resistance to vertical pull and little or no resistance to lateral forces.

1= Poor- denture offers slight resistance to vertical pull and little or no resistance to lateral force.

0= No retention- when the denture is seated in place, it displaces itself.

Stability:

With gloved hands, the examiner will attempt to rock the seated dentures by placing alternate horizontal force at the cuspid and contralateral molar regions of the upper and lower dentures.

The examiner will score denture stability as 0 - 4 using the following criteria:

4= Excellent- when denture base offers no rocking on its supporting structures under pressure.

3= Good- when denture base has very slight rocking on its supporting structures under pressure.

2= Fair- when denture base has slight rocking on its supporting structures under pressure.

1= Poor- when denture base has moderate rocking on its supporting structures under pressure.

0= No stability- when denture base has extreme rocking under pressure.

Sum score (upper + lower denture) of <6 = dentures with poor retention and stability.

 GlaxoSmithKline	Document Name	208397 Clinical Protocol 2.docx		
	Type	Version	Document Identifier	Effective Date
	eldo_controlled	2.0; Most Recent; Effective; CURRENT	090032d580db1b91	24-Oct-2017 08:49:05
	Reason For Issue	Auto Issue		

Sodium-calcium mixed partial salt of poly(methylvinylether/maleic acid) and carboxymethylcellulose

208397

Final Clinical Protocol, 20 Oct 2017

Sum score (upper + lower denture) 6-9 = dentures with fair retention and stability.

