ITT	Intent-To-Treat
MedDRA	Medical Dictionary for Regulatory Activities
OST	Oral Soft Tissue
PP	Per-Protocol
PT	Preferred Term
SAE	Serious Adverse Event
SD	Standard Deviation
SE	Standard Error
SOC	System Organ Class
TEAE	Treatment Emergent Adverse Event
USA	United State of America

The purpose of this Statistical Reporting and Analysis Plan is to describe the planned analyses and outputs to be included in the Clinical Study Report (CSR) for Protocol 208397.

1 Summary of Key Protocol Information

The aim of this study is to establish a reliable methodology that is able to characterize the performance of the adhesive in terms of reducing food ingress in a food occlusion methodology where subjects are asked to eat peanuts in a controlled manner and the mass of peanut particles under the denture, post peanut consumption, is measured and compared.

This study will be conducted in subjects with complete maxillary and mandibular dentures.

This study will be conducted at Salus Research in the United States of America (USA).

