3.2 Subgroups/Stratifications

The subgroups defined in this study are as follows:

Low Kapur-Olshan group: Defined as a composite Kapur-Olshan score of 6-14 (clinically fair and good dentures) at screening.

High Kapur-Olshan group: Defined as a composite Kapur-Olshan score of 15-18 (clinically very good dentures) at screening.

Exploratory analysis will be performed on the above defined subgroups.

Stratification factors are not defined in this study.

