4.4 Analysis of Efficacy

4.4.1 Primary Endpoint

4.4.1.1 Primary Endpoint Definition

The primary endpoint is defined as the combined mass of peanuts under maxillary and mandibular dentures.

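### Does the SAP change the primary objective from the conventional pattern to continuous strips and no adhesive?

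*SAP*

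**What the plan says.** Protocol Section 2, Table 2-1, states the primary objective as peanut mass in "a food occlusion methodology when denture adhesive is applied per conventional pattern". Its first exploratory objective has the same endpoint but applies when "denture adhesive is applied per continuous strips pattern and when no adhesive is used".

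SAP 1.2 prints the continuous-strips and no-adhesive sentence in the primary row: "To evaluate the mass of peanut particles that migrate under the dentures during a food occlusion methodology when denture adhesive is applied per continuous strips" and so on. It prints the same sentence again in the first exploratory row. The protocol's conventional-pattern sentence does not appear there. SAP 1.2 sits under Section 1, headed "Summary of Key Protocol Information".

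A later exploratory row of SAP 1.2 still covers the adhesive "when applied per conventional pattern to no adhesive use for subjects in the low and high Kapur-Olshan subgroups". SAP 4.4.1.1 names no treatment: "The primary endpoint is defined as the combined mass of peanuts under maxillary and mandibular dentures".

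**The concern.** The study has two adhesive patterns and one control, and application pattern is a factor of real interest. The protocol's introduction names the application method as a key difference between the unsuccessful study at this site and the earlier successful ones. Which pattern is called primary is therefore not an empty question.

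The only readable SAP sentence that attaches the word primary to a treatment disagrees with the protocol. The SAP is also the later document (14 December 2017, against 20 October 2017 for the protocol). A report writer who lifted the objectives from it would label continuous strips and no adhesive as primary and give the pooled conventional-pattern result no objective of its own. In an open-label study, an undeclared difference of this kind could later look like a choice made with results in view.

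**Working it through.** No formula or stated figure is at issue. The check compares the two objective tables and then follows the primary endpoint through to the outputs.

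**1. The sentences.**

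| Row | Treatment named | Words |
|---|---|---|
| Protocol, primary | Conventional | 25 |
| Protocol, first exploratory | Continuous strips and no adhesive | 32 |
| SAP, primary | Continuous strips and no adhesive | 32 |
| SAP, first exploratory | Continuous strips and no adhesive | 32 |

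The last three rows are identical. The two protocol sentences share words 1 to 23 and part at word 24, where one says conventional and the other continuous. Such a long common opening makes it easy to pick up the wrong line.

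**2. The count.** Each document has 1 primary + 5 exploratory + 1 safety = 7 objective lines. All 7 are distinct in the protocol. In the SAP, 6 are distinct because one is printed twice. A single objective with a single endpoint cannot be both primary and exploratory, so the SAP table is faulty on its own terms. That points to a slip, not a decision.

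**3. Is a change declared?** SAP Section 5, Table 1, lists departures from the protocol's analysis plan. It covers only the ITT and PP definitions and mentions no change of objective.

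**4. Does the slip reach the analysis?**

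- Protocol 10.2.5 (Primary Analysis) calls for descriptive statistics of the combined mass by treatment group and singles out no pattern.
- SAP 4.4.1.2 does the same and rules out a formal primary analysis.
- SAP 4.5.1 does not list whole-population combined mass among the exploratory endpoints. In the body of the SAP that measure is the primary endpoint for all three treatments.
- The shell of Table 14.2.2.1 has columns for conventional, continuous strip and no adhesive. Columns lost: 0 of 3.
- SAP 4.6 and Table 16.1.9.1.1 give all pairwise differences with 95% intervals and no p-values. Contrasts lost: 0 of 3. Appendix 1 lists conventional versus no adhesive first.
- Both documents say there is no formal success criterion, so no error rate or decision rule depends on which objective comes first.

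**5. What is missing from SAP 1.2?** Only the pooled conventional-pattern objective on combined mass. Conventional versus no adhesive remains an objective in both Kapur-Olshan groups. The SAP's lower group is given as "Low Kapur-Olshan group: Defined as a composite Kapur-Olshan score of 6-14 (clinically fair and good dentures) at screening"; the upper is 15 to 18. Protocol 7.1.3 scores retention 0 to 5 and, for stability, says "The examiner will score denture stability as 0 - 4 using the following criteria". The maximum is 2 dentures × (5 + 4) = 18. A sum of at least 6 is required, so eligible scores run from 6 to 18, which is 13 values. The groups hold 9 (6 to 14) and 4 (15 to 18), and 9 + 4 = 13. Every eligible subject falls under a retained objective.

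**The case for a change.** The strongest case for acting is that the primary objective is the last line a plan should get wrong, and that correcting it costs one sentence. Nothing else in the readable SAP puts it right: 4.4.1.1 names no treatment, and Appendix 1 orders the comparisons without calling any of them primary. The SAP says its purpose is to describe what goes into the CSR. Protocol 11.4 has the protocol's information posted publicly before enrolment, so a report that followed SAP 1.2 could differ from what was posted.

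The factual part stands: the two documents disagree and the SAP line is wrong. The consequence is weaker. It needs a report writer to prefer a summary of the protocol to the protocol itself, and no text directs that. Protocol 10.2 leaves to the SAP further detail of the analysis, not the objectives. A later date does not give the SAP authority over objectives it only claims to summarise. Even then the report would contain the same tables and estimates, with one label misplaced.

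The cause is also an inference. The text was extracted from a PDF, and other SAP tables show repeated content. In the SAP 1.3 treatment table the product name stands where the protocol has a row label. The shell of Table 14.2.1 shows four blocks of statistics although SAP 4.3.1 calls for three. These may be the author's errors or extraction errors, so the row should be read on the SAP page before anyone calls it an authoring mistake.

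**Conclusion.** The mismatch is real as the text reads, but it is clerical and nothing in the analysis turns on it. One of seven objective lines is wrong. No column of the primary table, pairwise difference, estimate, interval, error rate or decision rule is affected. An analyst working from SAP 4.4 and 4.6 and the table shells would produce what the protocol calls for, and a report writer who takes the objectives from the protocol would label them correctly.

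This rests on two assumptions. The first is that no switch was intended, which the duplicated sentence and the silence of SAP Section 5 support; a deliberate switch would have to be declared, justified and reconciled across the two documents. The second is that the SAP's list of data displays (Attachment 1), an embedded file that could not be read, agrees with the shells in Appendix 1.

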1.3 Treatments

The detail of three treatments used in this cross-over study is as follows:

	Test Product (Conventional Application)	Test Product (Continuous Strip Application)	Negative Control
Super Poligrip Free Denture Adhesive Cream (USA Marketplace)	Super Poligrip Free Denture Adhesive Cream (USA Marketplace)	Super Poligrip Free Denture Adhesive Cream (USA Marketplace)	No Adhesive
Product Formulation Code	CCI	CCI	N/A
Dose	1.6 gram (g) of adhesive applied as 1.0g for maxillary denture and 0.6g for	1.6g of adhesive applied as 1.0g for maxillary denture and 0.6g for mandibular	N/A

	Test Product (Conventional Application)	Test Product (Continuous Strip Application)	Negative Control
	mandibular denture.	denture.	
Route of Administration	Applied to the denture which is placed in mouth	Applied to the denture which is placed in mouth	N/A
Dose Instructions	As per the product application instructions	As per the product application instructions	N/A

A single, common adhesive will be used (Super Poligrip Free) with a common dose (1.6g) for both application methods. The adhesive will be extruded from a pre-dosed syringe following the application instructions. Super Poligrip Free has been selected as the adhesive in this study as it is a currently marketed product and is considered a representative denture adhesive. 1.6g of adhesive per treatment will be applied to each subject's dentures, an amount consistent with that used in previous studies and will therefore facilitate comparison of data from this study with previous work. This dose will be split as 1.00 ± 0.05 g for the maxillary and 0.60 ± 0.05 g for the mandibular dentures in accordance with consumer's normal distribution of adhesive.

A no adhesive negative control treatment has been chosen to provide a continual reference point to allow interpretation of the results and to facilitate comparison of the results from this study with previous work, and is representative of a significant number of denture wearers who currently do not use an adhesive.

1.4 Sample Size Calculation

Since this is an exploratory methodology development study, no formal sample size calculation was conducted. CCI

[REDACTED]

Therefore, approximately 48 (maximum 50) healthy subjects with both maxillary and mandibular full dentures will be enrolled in this study. Subject recruitment will be controlled to ensure $50 \pm 10\%$ of the subjects will be in each of the low and high Kapur-Olshan groups

[the low Kapur-Olshan group is defined as a composite Kapur-Olshan score of 6-14 (clinically fair and good dentures) and the high Kapur-Olshan score as 15-18 (clinically very good dentures)].

2 Planned Analyses

2.1 Interim Analysis

No interim analysis is planned.

2.2 Final Analyses

The final planned primary analyses will be performed after the completion of the following sequential steps:

1. All subjects have completed the study as defined in the protocol.
2. All required database cleaning activities have been completed and database has been locked.

3 Considerations for Data Analyses and Data Handling Conventions

3.1 Baseline Definition

A baseline definition is not required for this trial as no baseline measurements are performed or required for the summaries and analysis.

3.2 Subgroups/Stratifications

The subgroups defined in this study are as follows:

Low Kapur-Olshan group: Defined as a composite Kapur-Olshan score of 6-14 (clinically fair and good dentures) at screening.

High Kapur-Olshan group: Defined as a composite Kapur-Olshan score of 15-18 (clinically very good dentures) at screening.

Exploratory analysis will be performed on the above defined subgroups.

Stratification factors are not defined in this study.

3.3 Centers Pools

Since this is single center study, pooling of center is not applicable.

3.4 Timepoints and Visit Windows

The timepoints and visits for this study are defined in the section “Schedule of Activities” of the protocol. Any deviation from the study schedule will be reviewed on case-by-case basis to determine whether the data should be excluded from the Per-Protocol (PP) population. A time window non-compliance listing will be produced for the Data Review Meeting (DRM).

4 Data Analysis

Data analysis will be performed by inVentiv Health Clinical. The statistical analysis software used will be SAS version 9.4 (Studio) or higher.

Prior to database closure a DRM will be conducted in which various aspects of the trial will be discussed and agreed.

In this study the date and time of start of treatment will be the date and time when dentures were inserted.

Unless otherwise described below, all listings will be produced for all randomized subjects.

4.1 Populations for Analysis

4.1.1 Subject Disposition

Screen failures will be defined as subjects who do not satisfy either of the inclusion or exclusion criteria and are not subsequently randomized. A summary table for number of subjects screened, number of screen failure subjects with reasons why not randomized (Table 14.1.1.1) will be presented. The percentage will be based on total number of screened subjects.

Subject disposition will also be summarized as the number and percentage of subjects in each of the defined analysis population, who complete the study, who discontinue the study and reason for discontinuation (Table 14.1.1.1). The summary table will be presented by treatment group and for all combined treatment group (Overall). The percentage will be based on total number of subjects randomized in each treatment and overall.

The subject disposition table by treatment sequence, period (Table 14.1.1.2) will also be presented. In this summary table, the number and percentage of subjects starting and completing each period with reason for not completing any of the periods will be presented. The percentage will be computed using the number of subjects starting each period as a denominator.

Subject disposition including the critical demographic data (age, sex, race), screening date, treatment start date, date of completion or withdrawal, subject status (completer, Yes/No) and the specific reason for discontinuation, will be listed in Listing 16.2.1.1 by treatment sequence for randomized subject and non-randomized subjects (Listing 16.2.1.2) separately.

4.1.2 Protocol Deviations

Major protocol deviations (including deviations related to study inclusion/exclusion criteria, conduct of the trial, patient management or patient assessment) will be summarized and listed.

Protocol deviations will be tracked by the study team throughout the conduct of the study. Data will be reviewed at the DRM prior to closure of the database to ensure all important deviations are captured and categorised.

Major deviations of the protocol procedures identified as liable to influence the outcomes of the study may include, but will not be necessarily limited to the following:

- Inclusion/Exclusion criteria
- Treatment non-compliance
- Treatment administration error
- Use of prohibited medications before and during the study which is deemed to affect the assessment of efficacy.
- Deviations likely to affect study outcomes.

Minor deviations will be identified as those not classified as major deviations.

More details on protocol deviations can be found in the Protocol Deviation Management Plan (PDMP) of this study.

The number and percentage of subjects with any major protocol deviations and with each type of major protocol deviations will be presented by treatment (Table 14.1.2) and listed in Listing 16.2.2.1. Any minor protocol deviations will be listed similarly (Listing 16.2.2.2).

4.1.3 Analysis Populations

The analysis population defined in this study as follows:

Population	Definition / Criteria	Analyses Evaluated
Safety Population	
• All randomized subjects.• Receive at least one dose of study treatment during the study.	Safety
Intent-To-Treat (ITT) Population	
• All randomized subjects.• Received at least one dose of study treatment during the study.• Consumed peanuts and have at least one mass of peanuts from both upper and lower dentures.	Efficacy
PP Population	
• Subset of ITT population.• All subjects who are assessed as sufficiently compliant with study procedures and restrictions.• Subjects with major protocol deviations will be excluded. Depending on the nature of the major protocol deviation and impact on the efficacy variable (s), subjects will be either completely excluded from PP population or only partially excluded from the PP analyses. This will be determined on a case-by-case basis.	Efficacy

NOTES :

- Please refer to Attachment 1: List of Data Displays which details the population to be used for each displays being generated.

The primary population for assessment of efficacy will be the ITT population. A PP analysis will be performed only if 10% or more of ITT subjects are excluded from PP population.

Exclusion of any data from the analyses will be determined during a DRM prior to database lock. Subjects completely excluded from any analysis population will be listed (Listing 16.2.3.1).

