10.2.2 Exclusion of Data from Analysis

Exclusion of any data from the analyses will be determined during a Blind Data Review Meeting prior to database lock. Any reasons for exclusion from an analysis population will be listed, if applicable.

The Per Protocol (PP) population will be a subset of the ITT population.

Subjects with a protocol violation that is deemed to affect efficacy for all efficacy assessments will be excluded from the PP population. Subjects with a protocol violation that is deemed to affect efficacy for only some (but not all) of the efficacy assessments will be part of the PP population, but their data will be excluded from the assessment at which the protocol violation occurred. A PP analysis will be performed only if 10% or more ITT subjects are excluded from PP population.

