4.4.1.3 Supportive Analyses

If there is more than 10% difference in the overall number of subjects between PP and ITT populations, a summary of the primary efficacy variable will be presented for all subjects in the PP population (Table 14.2.2.2).

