Sodium-calcium mixed partial salt of poly (methylvinylether/maleic acid) and carboxymethylcellulose

208397

Final Statistical Reporting and Analysis plan, 14 DEC 2017

Protocol 208397

Program Run Date: DDMMYYYY

Table 14.1.1.2
Subject Disposition by Treatment Sequence
All Screened Subjects

Study Population: All Screened Subjects (N=xxx)	A-B-C n (%)	A-C-B n (%)	B-A-C n (%)	B-C-A n (%)	C-A-B n (%)	C-B-A n (%)	Overall n (%)
TOTAL SUBJECTS SCREENED							
SUBJECTS NOT RANDOMIZED*							
DID NOT MEET STUDY CRITERIA							
---							xxx (xx.x)
---							xxx (xx.x)
SUBJECTS RANDOMIZED	xxx						
STARTED PERIOD 1	xxx (xx.x)						
COMPLETED PERIOD 1**	xxx (xx.x)						
DID NOT COMPLETE PERIOD 1**	xxx (xx.x)						
ADVERSE EVENT	xxx (xx.x)						
LOST TO FOLLOW-UP	xxx (xx.x)						

SAFETY POPULATION	xxx (xx.x)						
ITT POPULATION	xxx (xx.x)						
PP POPULATION	xxx (xx.x)						

* Percentages are based on number of screened subjects.

** Percentages are based on number of randomized subjects in each treatment sequence.

A = Conventional Application; B = Continuous Strip Application; C = No Adhesive.

Program: xxxxxxx.sas

Page x of y

Source: Filename

Programming Note: This table will list all reason for not completing the study period and will continue for all other study period.

Sodium-calcium mixed partial salt of poly (methylvinylether/maleic acid) and carboxymethylcellulose

208397

Final Statistical Reporting and Analysis plan, 14 DEC 2017

Protocol 208397

Program Run Date: DDMMYYYY

Table 14.1.2
Incidence of Major Protocol Deviations
All Randomized Subjects

Study Population: All Randomized Subjects (N=xxx)	Conventional Application n (%)	Continuous Strip Application n (%)	No Adhesive n (%)	Overall n (%)
SUBJECTS WITH AT LEAST ONE MAJOR PROTOCOL DEVIATION	xxx (xx.x)	xxx (xx.x)	xxx (xx.x)	xxx (xx.x)
MAJOR PROTOCOL DEVIATIONS NOT LEADING TO EXCLUSION FROM PP POPULATION	xxx (xx.x)	xxx (xx.x)	xxx (xx.x)	xxx (xx.x)
DEVIATION REASON 1	xxx (xx.x)	xxx (xx.x)	xxx (xx.x)	xxx (xx.x)

MAJOR PROTOCOL DEVIATIONS LEADING TO EXCLUSION FROM PP POPULATION	xxx (xx.x)	xxx (xx.x)	xxx (xx.x)	xxx (xx.x)
EXCLUDING ALL				
DEVIATION REASON 1	xxx (xx.x)	xxx (xx.x)	xxx (xx.x)	xxx (xx.x)

EXCLUDING STUDY PERIOD 1				
DEVIATION REASON 1	xxx (xx.x)	xxx (xx.x)	xxx (xx.x)	xxx (xx.x)

EXCLUDING STUDY PERIOD 2				
DEVIATION REASON 1	xxx (xx.x)	xxx (xx.x)	xxx (xx.x)	xxx (xx.x)

Program: xxxxxx.sas

Page x of y
Source: Filename

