[4] Further details of reasons for withdrawal.

Program: xxxxxx.sas

Page x of y
Source: Filename

Sodium-calcium mixed partial salt of poly (methylvinylether/maleic acid) and carboxymethylcellulose

208397

Final Statistical Reporting and Analysis plan, 14 DEC 2017

Protocol 208397

Program Run Date: DDMMYYYY

Listing 16.2.1.2
Subject Disposition
All Non-Randomized Subjects

Subject Number	Age/Sex/Race[1]	Screening Date	Reason for Screen Failure	Further Details[2]
XXXXXX	XX/F/A1	DDMMYYYY	XXXXXX	XXXXXX

[1] Age in years; Sex: F = Female, M = Male; Race: A1 = African American/African Heritage, A2 = American Indian Or Alaskan Native,A3 = Asian-Central/South Asian Heritage, A4 = Asian-East Asian Heritage, A5 = Asian-Japanese Heritage, A6 = Asian-South East Asian Heritage, N = Native Hawaiian Or Other Pacific Islander, W1 = White-Arabic/North African Heritage, W2 = White - White/Caucasian/European Heritage, MT = Multiple Races.

[2] Further details of reasons for screen failure.

Program: xxxxxx.sas

Page x of y
Source: Filename

Sodium-calcium mixed partial salt of poly (methylvinylether/maleic acid) and carboxymethylcellulose

208397

Final Statistical Reporting and Analysis plan, 14 DEC 2017

Protocol 208397

Program Run Date: DDMMYYYY

Listing 16.2.2.1
Major Protocol Deviations
All Randomized Subjects

Treatment Sequence: A-B-C			
Subject	Age/Sex/Race [1]	Period(s) Excluded from PP Population	Deviation Reason
XXXXXX	PPD	All	PPD
XXXXXX		Period 1 only	
XXXXXX		From Period 2	

[1] Age in years; Sex: F = Female, M = Male; Race: A1 = African American/African Heritage, A2 = American Indian Or Alaskan Native, A3 = Asian-Central/South Asian Heritage, A4 = Asian-East Asian Heritage, A5 = Asian-Japanese Heritage, A6 = Asian-South East Asian Heritage, N = Native Hawaiian Or Other Pacific Islander, W1 = White-Arabic/North African Heritage, W2 = White - White/Caucasian/European Heritage, MT = Multiple Races.
A = Conventional Application; B = Continuous Strip Application; C = No Adhesive.

Program: xxxxxx.sas

Page x of y
Source: Filename

Programming Note: This listing is based on some of the details in the population definition document.

Sodium-calcium mixed partial salt of poly (methylvinylether/maleic acid) and carboxymethylcellulose

208397

Final Statistical Reporting and Analysis plan, 14 DEC 2017

Protocol 208397

Program Run Date: DDMMYYYY

Listing 16.2.2.2
Minor Protocol Deviations
All Randomized Subjects

Treatment Sequence: A-B-C

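### Is it unclear whether subjects who lose only one period count towards the 10% trigger for the per-protocol summary?

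*SAP*

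**What the plan says.** The trigger appears three times.

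- Protocol 10.2.2: "A PP analysis will be performed only if 10% or more ITT subjects are excluded from PP population".
- SAP 4.1.3: "A PP analysis will be performed only if 10% or more of ITT subjects are excluded from PP population".
- SAP 4.4.1.3 applies it to the PP version of the primary summary (Table 14.2.2.2), with a condition that begins "If there is more than 10% difference in the overall number of subjects between PP and ITT populations".

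On partly affected subjects, protocol 10.2.2 says that those whose violation touches only some efficacy assessments "will be part of the PP population, but their data will be excluded from the assessment at which the protocol violation occurred". SAP 4.1.3 opens by excluding subjects with major deviations, then divides them: "subjects will be either completely excluded from PP population or only partially excluded from the PP analyses". The choice is made case by case at the data review meeting before database lock.

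Two shells in SAP Appendix 1 use looser language. Table 14.1.2 has a block headed "MAJOR PROTOCOL DEVIATIONS LEADING TO EXCLUSION FROM PP POPULATION", which contains a row for exclusion of everything and rows such as "EXCLUDING STUDY PERIOD 1". Listing 16.2.2.1 has a column headed "Period(s) Excluded from PP Population", where one of the sample entries is a single period.

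**The concern.** In a three-period crossover, losing one visit is the natural form of PP exclusion. Many compliance rules apply visit by visit: the wait after denture insertion, the syringe mass and storage limit, and the interval between visits. If such losses do not count, the trigger can stay at zero while a fair amount of mass data is dropped. If they do count, as the shell headings suggest, a handful of one-visit deviations is enough to bring in the PP table.

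The Table 14.1.2 shell makes this look like more than a slip. It also has a contrasting block for major deviations that do not lead to PP exclusion, and it places one-period subjects in the other block, although protocol 10.2.2 keeps them in the population. Because full or partial exclusion is judged case by case in an open-label study, that judgement alone could decide whether the primary endpoint is summarised again without the data considered unreliable. The differing thresholds add a second apparent inconsistency.

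**Working it through.** **Inputs.** Planned N is about 48, maximum 50 (protocol 10.1, SAP 1.4). There are three periods per subject (protocol section 3), so 48 × 3 = 144 subject-periods. The 10% is a stipulated rule, so there is no derived figure to reproduce. The documents give no deviation rate. The counts below are illustrations that assume an ITT population of 48 with complete data.

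**Does the reading affect the decision?** Let c be the number of subjects fully excluded and p the number losing one period.

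- Reading A (whole subjects only) = c/48
- Reading B (any exclusion) = (c + p)/48
- Share of records dropped = (3c + p)/144

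| c | p | Reading A | Reading B | Records dropped |
|---|---|---|---|---|
| 0 | 5 | 0/48 = 0%, off | 5/48 = 10.4%, on | 5/144 = 3.5% |
| 4 | 1 | 4/48 = 8.3%, off | 5/48 = 10.4%, on | 13/144 = 9.0% |
| 0 | 16 | 0/48 = 0%, off | 16/48 = 33.3%, on | 16/144 = 11.1% |
| 5 | 0 | 5/48 = 10.4%, on | 5/48 = 10.4%, on | 15/144 = 10.4% |

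So the reading can change whether Table 14.2.2.2 is produced.

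**Which reading does the plan adopt?**

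1. Protocol 10.2.2 places a partly affected subject inside the PP population and, in the same paragraph, counts subjects outside it. That is reading A.
2. SAP 4.1.3 keeps the same split: complete exclusion is from the population, partial exclusion is from the analyses. The trigger refers to the population.
3. SAP 4.4.1.3 compares numbers of subjects. Since PP is a subset of ITT, N(ITT) − N(PP) is the number of ITT subjects wholly outside PP. That is c, again reading A.
4. Other displays agree. Listing 16.2.3.1 is for complete exclusions and has one PP entry per subject, and Table 14.1.1.1 reports PP as a single subject count.
5. SAP Section 5 records the revised population definitions and lists no change to the trigger.

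Against these stand two shell headings. Neither shell states or refers to the trigger, and both separate whole-subject from period-level exclusion in their rows or entries.

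**Threshold wording.** Smallest number of exclusions that satisfies each form:

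| N | 10% or more | more than 10% |
|---|---|---|
| 40 | 4 (10.0%) | 5 (12.5%) |
| 41–49 | 5 | 5 |
| 48 | 5 (10.4%) | 5 (10.4%) |
| 50 | 5 (10.0%) | 6 (12.0%) |

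The two forms differ only when exactly 10% are excluded.

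**Would a different trigger do better?** One candidate is to produce the PP table when 10% or more of the values for any one treatment are excluded. It would catch losses concentrated in one arm. But 12 subjects each losing one period, spread 4/4/4 over the treatments, are 12/48 = 25% of subjects and only 4/48 = 8.3% per treatment, so this rule would stay silent too. It would also depart from protocol 10.2.2.

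**The case for a change.** The strongest case for a change is that a subject count is a poor gauge of lost data in a crossover. Under reading A, 16 subjects losing 16 records leave the PP table off, while five subjects losing 15 records turn it on. With whole-visit exclusions, and every subject keeping one visit, 48 × 2 = 96 of 144 records (66.7%) could go with the trigger still at zero. No sentence says outright that partial exclusions do not count, and the people deciding full or partial status know the treatments.

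The arithmetic stands, as does the remark that the SAP leaves the counting rule to be inferred. But the insensitivity is a property of a rule the plan chose, and each alternative trigger has blind spots of its own. The large-loss cases are constructed extremes in a single-centre study where treatment application is supervised by site staff. The discretion is not open-ended: protocol 10.2.2 asks whether a violation affects all or only some efficacy assessments, and the answer is fixed before database lock. Some of the specification is also outside the public text (the deviation management plan, the population definition document and the list of displays), so a written counting convention may exist there.

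**Conclusion.** No change to the plan follows. An analyst following protocol 10.2.2 and SAP 4.1.3 and 4.4.1.3 would count completely excluded subjects, which at 48 ITT subjects means five or more. What remains is clerical: two shell headings that say population where analysis is meant, and a threshold mismatch with no effect at 48 subjects and a one-subject effect at 40 or 50.

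The consequence is small on either reading. Only Table 14.2.2.2, a supportive descriptive summary, depends on the trigger. ITT is the primary population, the study has no success criterion, and SAP 4.6 reports no p-values. Listing 16.2.2.1 shows which periods were excluded and Listing 16.2.6.1 gives the masses by period, so a reader of the study report could rebuild the PP summary even if it were not produced.

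This rests on taking the operative sections over the mock-up headings, and on an ITT population near the planned 48. Replacing the subject count with a share of records or a per-treatment rule is a matter of preference and shows no clear gain.
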